#### 5.4.2 Prohibited Concomitant Medications

Participants are prohibited from receiving the following therapies during the Screening and Treatment Phase (including retreatment for post-complete response relapse) of this trial:

- Immunotherapy not specified in this protocol
- Chemotherapy not specified in this protocol
- Investigational agents other than pembrolizumab
- (PembroRT Cohort only) Live vaccines within 30 days prior to the first dose of study treatment and while participating in the study. Examples of live vaccines include, but are not limited to, the following: measles, mumps, rubella, varicella/zoster, yellow fever, rabies, BCG, and typhoid vaccine. Seasonal influenza vaccines for injection are generally killed virus vaccines and are allowed; however, intranasal influenza vaccines (e.g., FluMist®) are live attenuated vaccines and are not allowed.

- Systemic glucocorticoids for any purpose other than to modulate symptoms from an event of clinical interest of suspected immunologic etiology. The use of physiologic doses of corticosteroids may be approved after consultation with the Sponsor.

Participants who, in the assessment by the investigator, require the use of any of the aforementioned treatments for clinical management should be removed from the study. All treatments that the Investigator considers necessary for a participant's welfare may be administered at the discretion of the Investigator in keeping with the community standards of medical care.

Medications or vaccinations specifically prohibited in the exclusion criteria are not allowed during the ongoing study. If there is a clinical indication for any medication or vaccination specifically prohibited during the study, discontinuation from study therapy or vaccination may be required. The final decision on any supportive therapy or vaccination rests with the investigator and/or the participant's primary physician. However, the decision to continue the participant on study treatment requires the agreement of the investigator, the Sponsor and the participant.

There are no prohibited therapies during the Post-Treatment Follow-up Phase.

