#### **4.6.2.2 Safety Endpoints**

- Severe (grade  $\geq 3$ ) adverse events, scored using CTCAE v 4.03.
  - It will be important to characterize the toxicity profile of sequential pembrolizumab and radiotherapy for locally advanced NSCLC, as this is a novel treatment approach.
- Pneumonitis (grade  $\geq 2$ ).
  - It will be important to characterize the rate of pneumonitis, which may occur because of radiotherapy or immunotherapy, for study subjects.
- Patient-reported treatment-related toxicity, scored using PRO-CTCAE.
  - See Section 4.5
- Unplanned hospitalization.
  - Many patients treated with radiotherapy or chemoradiotherapy for locally advanced NSCLC are hospitalized due to treatment toxicity. It will be important to characterize the hospitalization rate for patients treated with pembrolizumab and radiotherapy for locally advanced NSCLC.
- Daily step counts, measured using wearable fitness trackers.
  - See Section 4.4

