**Table 3 Dose modification and toxicity management guidelines for immune-related AEs associated with pembrolizumab**

General instructions:				
Immune-related AEs	Toxicity grade or conditions (CTCAEv4.0)	Action taken to pembrolizumab	irAE management with corticosteroid and/or other therapies	Monitor and follow-up
Pneumonitis	Grade 2	Withhold	
 
Administer corticosteroids (initial dose of 1-2 mg/kg prednisone or equivalent) followed by taper
 
	
 
Monitor participants for signs and symptoms of pneumonitis
 
Evaluate participants with suspected pneumonitis with radiographic imaging and initiate corticosteroid treatment
 
Add prophylactic antibiotics for opportunistic infections
 

	Grade 3 or 4, or recurrent Grade 2	Permanently discontinue		
Diarrhea / Colitis	Grade 2 or 3	Withhold	
 
Administer corticosteroids (initial dose of 1-2 mg/kg prednisone or equivalent) followed by taper
 
	
 
Monitor participants for signs and symptoms of enterocolitis (ie, diarrhea, abdominal pain, blood or mucus in stool with or without fever) and of bowel perforation (ie, peritoneal signs and ileus).
 
Participants with <math>\geq</math> Grade 2 diarrhea suspecting colitis should consider GI consultation and performing endoscopy to rule out colitis.
 
Participants with diarrhea/colitis should be advised to drink liberal quantities of clear fluids. If sufficient oral fluid intake is not feasible, fluid and electrolytes should be substituted via IV infusion.
 

	Grade 4	Permanently discontinue		

AST / ALT elevation or Increased bilirubin	Grade 2	Withhold	
 
Administer corticosteroids (initial dose of 0.5- 1 mg/kg prednisone or equivalent) followed by taper
 
	
 
Monitor with liver function tests (consider weekly or more frequently until liver enzyme value returned to baseline or is stable)
 

	Grade 3 or 4	Permanently discontinue	
 
Administer corticosteroids (initial dose of 1-2 mg/kg prednisone or equivalent) followed by taper
 
	

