### 7.2.3.2 Events of Clinical Interest

Selected non-serious and serious adverse events are also known as Events of Clinical Interest (ECI) and must be reported within 2 working days to Merck Global Safety. (Attn: Worldwide Product Safety; [contact]).

For the time period beginning when the consent form is signed until treatment allocation/randomization, any ECI, or follow up to an ECI, that occurs to any participant must be reported within 2 working days to Merck Global Safety if it causes the participant to be excluded from the trial, or is the result of a protocol-specified intervention, including but not limited to washout or discontinuation of usual therapy, diet, placebo treatment or a procedure.

For the time period beginning at treatment allocation through 90 days following cessation of treatment, or 30 days following cessation of treatment if the participant initiates new anticancer therapy, whichever is earlier, any ECI, or follow up to an ECI, whether or not related to Merck product, must be reported within 2 working days to Merck Global Safety.

Events of clinical interest for this trial include:

1. an overdose of Merck product, as defined in Section 7.2.1 - Definition of an Overdose for This Protocol and Reporting of Overdose to the Sponsor, that is not associated with clinical symptoms or abnormal laboratory results.
2. an elevated AST or ALT lab value that is greater than or equal to 3X the upper limit of normal and an elevated total bilirubin lab value that is greater than or equal to 2X the upper limit of normal and, at the same time, an alkaline phosphatase lab value that is less than 2X the upper limit of normal, as determined by way of protocol-specified laboratory testing or unscheduled laboratory testing.\*

\*Note: These criteria are based upon available regulatory guidance documents. The purpose of the criteria is to specify a threshold of abnormal hepatic tests that may require an additional evaluation for an underlying etiology.

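### The steroid ban and removal sentence in 5.4.2 do not fit Table 3, 5.5 or 7.2.3.2, and could end follow-up after treated pneumonitis

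*Combined protocol and SAP*

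**What the plan says.** Section 5.4.2 lists therapies prohibited in the Screening and Treatment Phase. One entry is "Systemic glucocorticoids for any purpose other than to modulate symptoms from an event of clinical interest of suspected immunologic etiology"; physiologic doses may be approved after consulting the sponsor. The live-vaccine entry is marked as PembroRT only. The steroid entry carries no cohort label. Participants who, in the investigator's assessment, "require the use of any of the aforementioned treatments for clinical management should be removed from the study".

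The same section also contains softer sentences: "All treatments that the Investigator considers necessary for a participant's welfare may be administered at the discretion of the Investigator"; "discontinuation from study therapy or vaccination may be required"; and "the decision to continue the participant on study treatment requires the agreement of the investigator, the Sponsor and the participant". It closes by lifting all prohibitions in post-treatment follow-up.

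For pneumonitis, Table 3 says "Administer corticosteroids (initial dose of 1-2 mg/kg prednisone or equivalent) followed by taper". Pembrolizumab is withheld at Grade 2 and permanently stopped at Grade 3 or 4 or recurrent Grade 2. Section 5.4.3 endorses oral or IV corticosteroids under Table 3, but only for events judged related to pembrolizumab.

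Section 7.2.3.2 opens its list with "Events of clinical interest for this trial include" and gives two items: an overdose without symptoms or abnormal laboratory results, and a combined liver-test abnormality.

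Section 5.5 says that participants stopped for unacceptable adverse experiences or recurrent Grade 2 pneumonitis, among other reasons, leave study treatment but remain monitored in the study.

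On the endpoint, 4.6.2.2 says "It will be important to characterize the rate of pneumonitis, which may occur because of radiotherapy or immunotherapy". Secondary objective 6 compares pneumonitis rates between the cohorts.

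**The concern.** The rule that decides who leaves the study is tied to treatment for a toxicity that the study sets out to compare. A site that follows the removal sentence would lose a participant because pneumonitis was treated with a steroid, and with that participant the later progression, survival and toxicity data. A site that follows 5.5 or the softer sentences would keep the same participant. Follow-up would then depend on which sentence a site reads. Sites also hold conflicting instructions on steroid use itself.

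**Working it through.** The plan states no figure on this point, so the check sets the sections side by side.

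1. **What the exception covers, read literally.** It has two joined conditions: the event must be an event of clinical interest, and it must be of suspected immunologic origin. The first is a defined term. Section 5.4.1, in the same part of the protocol, uses it with a pointer to the definitions in 7.2. The list in 7.2.3.2 does not contain pneumonitis, colitis, nephritis, hypophysitis or myocarditis, and Table 3 directs corticosteroids for each of them. Table 4 also lists corticosteroids for Grade 3 or 4 infusion reactions. On this reading 5.4.2 conflicts with Table 3, Table 4 and 5.4.3.

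2. **What it covers, read by purpose.** If any suspected immune event qualifies, the conflict with Table 3 disappears. Pneumonitis attributed to radiotherapy still has no exception: it is not of suspected immunologic origin, and 5.4.3 confines the Table 3 guidance to pembrolizumab-related events. Yet 4.6.2.2 names radiotherapy as one of the two causes of the endpoint. The gap therefore remains on either reading, during the Treatment Phase.

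3. **Which cohort.** The missing label, beside a labelled live-vaccine entry, makes the steroid entry apply to both cohorts. Exclusion criterion 13d, by contrast, restricts chronic systemic steroids only for patients receiving pembrolizumab. The intended scope is not settled.

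4. **What follows from needing a steroid.** The removal sentence takes the participant out of the study. Section 5.5 stops treatment and continues monitoring. The softer sentences in 5.4.2 concern giving a treatment or continuing study therapy; none says what happens to follow-up. Under 7.1.3.1, a participant who discontinues or withdraws early has the final-visit activities done at that time. Section 8.1 gives a PFS censoring rule for loss to follow-up and none for removal.

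5. **When it applies.** The ban ends with the Treatment Phase, which is not defined by cohort.
   - PembroRT treatment runs about one year (Trial Summary; 5.5). As far as the flow chart can be read, radiotherapy falls in about weeks 10 to 16 and the last column is week 51. The radiotherapy adverse-event text in 5.2.3 places radiographic lung change typically within six months, about 26 weeks, of treatment. 16 + 26 = 42, which is before week 51.
   - ChemoRT radiotherapy is 20 to 37 fractions. At the five per week marked in the flow chart, that is 20/5 = 4 to 37/5 = 7.4 weeks. Adjuvant therapy is optional, and the protocol does not say whether it belongs to the Treatment Phase.

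   The ban could therefore cover the months after radiotherapy in PembroRT and few or none of them in ChemoRT.

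6. **Size.** One PembroRT participant is 1/25 = 4% of the primary cohort. The documents give no expected rate of steroid-treated pneumonitis, so nothing further can be calculated.

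**The case against.** The strongest reply is that the exception names suspected immunologic cause, which is what Table 3 is about, and that 5.4.3 endorses steroids under Table 3. The list in 7.2.3.2 serves rapid reporting to the drug supplier and is not a list of treatable conditions. One of its items is an overdose without symptoms, so an exception for modulating symptoms would cover almost nothing if confined to that list. This stands to the extent that the conflict with Table 3 arises only on the literal reading. It does not remove the gap for pneumonitis attributed to radiotherapy.

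The documents also presuppose that patients stay. Table 3 and 5.5 both provide for recurrent Grade 2 pneumonitis, which implies that the participant remained after a first episode. Sections 7.1.2.6.2 and 7.1.5.2 continue imaging after treatment stops for reasons other than progression. That shows the likely intention, and also that the removal sentence contradicts it: those sections deal with stopping treatment, not with leaving the study.

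A reader might infer that the exception can never apply in ChemoRT. The documents do not support that, because 5.2.2 allows adjuvant immunotherapy in that cohort and the exception does not mention pembrolizumab. A reader might also infer that the pneumonitis rate itself would be lost. It would not, because the event that prompts the steroid is recorded before any removal.

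**Conclusion.** The wording is inconsistent and should be corrected. Three parts hold: the removal sentence contradicts 5.5 and sits badly with other sentences in 5.4.2; pneumonitis attributed to radiotherapy during the Treatment Phase has no exception in either cohort; and the exception conflicts with Table 3 if its key term takes the 7.2.3.2 meaning.

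What is at risk is PFS, survival and toxicity follow-up after removal, at 4% of the primary cohort per PembroRT participant. The loss may be unequal between cohorts, on the assumption that the Treatment Phase is much longer in PembroRT.

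A reader might go on to infer a definite inflation of one-year PFS or of the false-positive rate. That would require removal to coincide with progression or death, and no section links the need for steroids to either. No such figure can be given.

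**What to change.** In one amendment, reconcile 5.4.2 with Table 3, Table 4, 5.4.3, 5.5 and 7.2.3.2. Say which cohort or cohorts the steroid entry covers, how it applies to pneumonitis attributed to radiotherapy, and whether optional ChemoRT adjuvant therapy belongs to the Treatment Phase. When steroids may be used, and what then happens to study treatment, is for the sponsor to decide.

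Replace the removal sentence with wording consistent with 5.5, stating that use of a prohibited medication, steroids included, does not end follow-up for PFS, survival or safety. Repeat this in 8.1 so that steroid use is not treated as a reason to censor. Section 7.1.5.3 already moves participants who start new anticancer therapy into telephone survival follow-up, so the new sentence should say how the two fit together. Also correct the references in 5.4.3 that place Table 3 in 5.2.2, which is the chemotherapy section.

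The cost is protocol wording only, with no added visits or data collection.

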#### **5.5 Participant Withdrawal/Discontinuation Criteria**

Participants may discontinue study treatment at any time for any reason or be dropped from the study treatment at the discretion of the investigator should any untoward effect occur. In addition, a participant may be discontinued from study treatment by the investigator or the Sponsor if study treatment is inappropriate, the trial plan is violated, or for administrative

and/or other safety reasons. Specific details regarding procedures to be performed at study treatment discontinuation are provided in Section 7.1.4 – Other Procedures.

A participant must be discontinued from study treatment but continue to be monitored in the study for any of the following reasons:

- The participant or participant's legally acceptable representative requests to discontinue study treatment
- Confirmed radiographic disease progression outlined in Section 7.1.2.6
- Unacceptable adverse experiences as described in Section 5.2.2.
- The participant has a medical condition or personal circumstance which, in the opinion of the investigator and/or sponsor, placed the participant at unnecessary risk from continued administration of study treatment.
- The participant has a confirmed positive serum pregnancy test
- Recurrent Grade 2 pneumonitis
- The participant is lost to follow-up
- Completion of 15 treatments (approximately 1 year) with pembrolizumab

Note: The number of treatments is calculated starting with the first dose. Participants who stop the combination or pembrolizumab after receiving 15 doses may be eligible for retreatment if they progress after stopping study treatment. Participants may be retreated in the Second Course Phase (Retreatment) for up to an additional 17 cycles (approximately 1 year).

- Administrative reasons

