#### **7.1.2.6.2 End of Treatment and Follow-up Tumor Imaging**

In participants who discontinue study treatment, tumor imaging should be performed at the time of treatment discontinuation ( $\pm 4$ -week window). If previous imaging was obtained within 4 weeks prior to the date of discontinuation, then imaging at treatment discontinuation is not mandatory. In participants who discontinue study treatment due to documented disease progression and the Investigator elects not to implement iRECIST, this is the final required tumor imaging.

In participants who discontinue study treatment without documented disease progression, every effort should be made to continue monitoring their disease status by tumor imaging using the same imaging schedule used while on treatment.

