### 7.1.5.2 Follow-up Visits

Participants who discontinue study treatment for a reason other than disease progression will move into the Follow-Up Phase and should be assessed every 12 weeks ( $84 \pm 7$  days) by radiologic imaging to monitor disease status. Every effort should be made to collect information regarding disease status. Information regarding post-study anti-cancer treatment will be collected if new treatment is initiated.

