### 7.1.5.3 Survival Follow-up

Participants who experience confirmed disease progression or start a new anticancer therapy, will move into the Survival Follow-Up Phase and should be contacted by telephone every 12 weeks to assess for survival status until death, withdrawal of consent, or the end of the trial, whichever occurs first.

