## 8.0 STATISTICAL ANALYSIS PLAN

### 8.1 Statistical Analysis Plan – Primary Endpoint and Sample Size Calculation

The **primary endpoint** is progression-free survival (PFS) in the PembroRT cohort one year following study enrollment. PFS duration will be defined as the time from study registration to the date of disease progression or death from any cause. In cases where a scan is concerning for progressive disease based on RECIST 1.1 criteria, and progression is confirmed on a subsequent scan 4-8 weeks later (satisfying iRECIST criteria for progression), the date of disease progression would be the date of the first scan demonstrating progression. PFS rates will be estimated using the Kaplan-Meier Survival method, from which the probability of PFS at various time points and corresponding 95% confidence intervals will be estimated. If a patient is lost to follow-up without having disease progression, progression-free survival will be censored at the date of the patient's last clinic visit. Based on published multi-institutional trials and data from our institution, we expect the one-year progression-free survival rate ( $H_0$ ) to be to 40% with standard chemoradiotherapy. We hypothesize that this rate will be at least 65% ( $H_1$ ) for subjects in the PembroRT cohort. A one sample two-sided log-rank test will be used to compare the one-year PFS rate in the PembroRT cohort against the expected rate with ChemoRT. We plan to accrue **25 subjects to the PembroRT cohort**. Assuming that the accrual period will last 18 months and that event rates will follow an exponential distribution, this sample size will provide 81% power to detect an improvement in PFS at 1 year at a 5% level of significance using a one sample two-sided log-rank test [48, 49].

The ChemoRT cohort will be open to accrual while accrual to the PembroRT cohort is ongoing. We expect that approximately 40% of patients with locally advanced NSCLC have PD-L1 expression of at least 50%. We therefore expect that approximately 38 subjects will be enrolled and treated with standard concurrent chemoradiotherapy as part of this trial, which will yield a **total sample size of approximately 63 subjects**.

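### Section 5.4.2 removes participants who need a prohibited therapy from the study, in conflict with the follow-up sections, and 8.1 does not say how PFS treats them

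*Combined protocol and SAP*

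**What the plan says.** **Section 5.4.2 (prohibited medications).** The list covers immunotherapy and chemotherapy outside the protocol, other investigational agents, live vaccines (PembroRT only), and systemic glucocorticoids other than for events of suspected immune origin. It applies during the Screening and Treatment Phase; nothing is prohibited in post-treatment follow-up. Participants who "require the use of any of the aforementioned treatments for clinical management should be removed from the study". A later paragraph of the same section says that "discontinuation from study therapy or vaccination may be required". It adds that keeping a participant on study treatment needs the agreement of the investigator, the Sponsor and the participant.

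**Section 5.5 (discontinuation).** On plan violations, "a participant may be discontinued from study treatment by the investigator or the Sponsor if study treatment is inappropriate, the trial plan is violated". For a listed set of reasons, "A participant must be discontinued from study treatment but continue to be monitored in the study for any of the following reasons". Need for a prohibited therapy is not on that list.

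**Sections 7.1.2.6.2, 7.1.5.2 and 7.1.5.3 (follow-up).** For those who stop treatment without documented progression, "every effort should be made to continue monitoring their disease status by tumor imaging". Likewise, "Participants who discontinue study treatment for a reason other than disease progression will move into the Follow-Up Phase", with imaging every 12 weeks. Those who have confirmed progression or "start a new anticancer therapy, will move into the Survival Follow-Up Phase and should be contacted by telephone every 12 weeks".

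**Section 8.1 (primary analysis).** PFS runs from registration to progression or death from any cause. One censoring rule is given: "If a patient is lost to follow-up without having disease progression, progression-free survival will be censored at the date of" the last clinic visit. Nothing is said about removal from the study, prohibited therapy or new anticancer therapy before progression, and no sensitivity analysis is planned.

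**The concern.** For one trigger, 5.4.2 gives three possible outcomes: leave the study, stop study treatment, or stay on treatment by agreement. Only the first ends follow-up, and it is the only one that departs from the rest of the protocol.

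The trigger is unlikely to be neutral. Chemotherapy or immunotherapy outside the protocol, begun before progression is documented, plausibly marks a participant who is doing badly. Some steroid use outside the immune-event exemption may do so too. If such participants leave the study and the analyst censors them for want of another rule, censoring is tied to the outcome and the Kaplan-Meier curve for PembroRT is too high. The primary test compares that single cohort of 25 with a fixed 40%, so no concurrent arm in the test shares the bias. Removal would also end survival and safety follow-up, which matters for the secondary objectives on overall survival, severe adverse events and pneumonitis.

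**Working it through.** **1. Reading the sections together.**

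| Section | Trigger | Treatment | Follow-up |
|---|---|---|---|
| 5.4.2, removal sentence | needs a prohibited therapy | – | ends |
| 5.4.2, later paragraph | needs a prohibited therapy | may have to stop; may continue by agreement | not addressed |
| 5.5 | plan violated | may stop | not ended |
| 5.5 | listed reasons | must stop | continues |
| 7.1.2.6.2, 7.1.5.2 | stopped without progression | stopped | imaging continues |
| 7.1.5.3 | confirmed progression or new anticancer therapy | – | telephone, survival only |

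The conflict is direct within 5.4.2 and against 7.1.2.6.2, 7.1.5.2 and 7.1.5.3. Against 5.5 it is by overlap, through unacceptable adverse experiences, medical condition or administrative reasons.

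**2. The plan's own figure.** Inputs from 8.1: n = 25, one-year PFS 40% against 65%, exponential, 18-month accrual, two-sided 5%, one-sample log-rank. Follow-up after accrual is not stated; I assume 12 months.
- Hazards per year: λ0 = −ln 0.40 = 0.916; λ1 = −ln 0.65 = 0.431.
- Under 65%, with follow-up uniform on 1 to 2.5 years, the probability of an observed event is p = 1 − (e^(−0.431×1) − e^(−0.431×2.5))/(0.431×1.5) = 0.521.
- Expected events per participant at the null hazard: e0 = p × λ0/λ1 = 0.521 × 0.916/0.431 = 1.109.
- Power for Z = (O−E)/√E is Φ{[√n(e0−p) − 1.96√e0]/sd}, where sd = 1.012 is the standard deviation of one participant's contribution to O−E. This is Φ{[5 × 0.587 − 1.96 × 1.053]/1.012} = Φ(0.863) = 80.6%.

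The stated 81% is reproduced. The variance form (O+E)/2 gives 87.6% with 12 months of follow-up and 80.6% with 6 months, so the form used is not settled. Both are carried below.

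**3. If removed participants are censored.** Let q be the share of first-year failures removed and censored at the moment of failure. The documents give no value for q. First-year failures are used because the prohibition covers only the Screening and Treatment Phase and pembrolizumab lasts about one year (Sections 1.0 and 5.5).
- The observed hazard over the first year falls to (1−q)λ0, so apparent one-year PFS tends to 0.40^(1−q).
- At 40% PFS, first-year failures number about 25 × 0.60 = 15, so about 15q participants are removed.
- The chance of falsely declaring benefit (Z < −1.96) comes from 200,000 simulated trials per setting.

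| q | Removed | Apparent one-year PFS | False benefit, E form | False benefit, (O+E)/2 form |
|---|---|---|---|---|
| 0 | 0 | 40% | 1.6% | 2.7% |
| 10% | 1.5 | 0.40^0.9 = 44% | 3.5% | 5.6% |
| 20% | 3 | 0.40^0.8 = 48% | 7.1% | 10.7% |
| 30% | 4.5 | 0.40^0.7 = 53% | 13.3% | 19.0% |

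Independent runs agree with these rates to about 0.1 percentage point. For a given q they sit at the high end, because every removed participant's event, deaths included, is assumed lost at the moment it would have occurred.

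**The case against.** The strongest reply is that the protocol already protects follow-up. Section 5.4.2 can be read as stopping treatment only, since its later paragraph speaks of stopping study therapy and even of continuing it. Sections 7.1.2.6.2 and 7.1.5.2 keep imaging going, 7.1.5.3 tracks deaths, 7.1.3.1 calls for final-visit activities at withdrawal, and 7.1.2.6 lets unscheduled scans establish progression. A site that follows these would lose few events. This stands as a limit on the likely size, but it does not remove the sentence that tells sites to take the participant off the study.

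Four stronger readings are tempting, and the documents do not support them.
- **That 8.1 censors removed participants.** Its rule is written for loss to follow-up. Applying it to removal is an inference; what the text shows is silence.
- **That these participants are dropped from the analysis.** A censored participant stays in the risk set until the censoring date; only later events are lost.
- **That everyone removed is a failing patient.** Progression documented before the new therapy already counts as an event, live vaccines do not signal failure, and steroids for suspected immune events are exempt.
- **That the false-positive rate could reach 23–31%.** That range results from applying a 30% share to all failures over the full follow-up of up to 30 months. Section 5.4.2 prohibits nothing in post-treatment follow-up, so the first-year figures are the relevant ones.

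**Conclusion.** The point holds as a conflict in the protocol combined with a gap in the analysis plan. The removal sentence in 5.4.2 contradicts softer wording in its own section and the follow-up sections, and 8.1 does not say what happens to PFS for the participants concerned. If they are censored, and if they tend to be failing, the bias favours PembroRT.

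The size depends wholly on an assumed removal share. Three removals among about 15 first-year failures would move apparent one-year PFS from 40% to 48% and the chance of a false claim of benefit from 1.6–2.7% to 7.1–10.7%. This assumes exponential PFS, 12 months of follow-up after accrual, and loss of every removed participant's event. The documents do not show that removals on this scale will occur. The change is worth making because a literal reading of the rule harms the primary endpoint and the wording is cheap to correct.

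**What to change.** - **Protocol 5.4.2, 5.5, 7.1.2.6.2, 7.1.5.2 and 7.1.5.3.** Reconcile these so that needing a prohibited therapy does not end follow-up for progression, survival and safety, whatever is decided about study treatment. Which treatment rule should apply is for the sponsor and investigators.
- **Protocol 7.1.5.3.** Correcting 5.4.2 alone would leave a gap: participants who start a new anticancer therapy before documented progression are scheduled only for telephone contact, so deaths are captured but progression may be missed. Keep them on the imaging schedule already in 7.1.2.6.2 and 7.1.5.2 until progression.
- **Section 8.1.** State that stopping study treatment, prohibited therapy or new anticancer therapy before progression is not by itself a reason to censor PFS. Add one sensitivity analysis that counts these as PFS events.

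The cost is a few sentences of amendment, one extra analysis, and continued scheduled imaging for a small number of participants. Sample size is unchanged, and with those events counted the design keeps its stated power of about 81%.
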